1. PROTOCOL SYNOPSIS

PROTOCOL TITLE	An Open Label Multi-Center Extension Study to Evaluate the Long-term Safety of Zorblisa TM (SD-101-6.0) in Patients with Epidermolysis Bullosa
PROTOCOL No.	SD-006
VERSION No.	3
SPONSOR	Scioderm, Inc. An Amicus Therapeutics Company [name]
INVESTIGATIONAL PRODUCT	ZORBLISA (SD-101-6.0)
PHASE OF DEVELOPMENT	Open Label Extension
INDICATION AND RATIONALE	The aim is to assess the long-term safety of topical use of ZORBLISA in patients with Epidermolysis Bullosa (EB).
STUDY DESIGN	This is an open label, multi-center extension study to assess the long-term safety of topically applied ZORBLISA in Patients with Simplex, Recessive Dystrophic, and Junctional non-Herlitz Epidermolysis Bullosa.
	ZORBLISA will be applied topically, once a day, to the entire body for a period of 1440 days. This study may be further extended by amendment until either SD-101 becomes commercially available or the clinical development of SD-101 in EB is discontinued.
	Patients who have successfully completed Study SD-005 (on study drug at Visit 5) will have the option to roll over into the SD-006 study. The baseline visit (Visit 1) will occur at Visit 5 for SD-005. The Body Surface Area (BSA) assessments of lesional skin and wound burden performed at the Visit 5 for SD-005 will be utilized as the baseline assessment for SD-006. Patients will return for follow-up visits at Months 1, 3, 6, 9, 12, 15, 18, 21, 24, 27, 30, 33, 36, 39, 42,

CONFIDENTIAL

45, and48 after Visit 1. At each visit, assessments will include BSAI of lesional skin and wound burden. For target wounds that are not closed by the end of Study SD-005, the ARANZ picture and calculation of target wound area at the final visit for Study SD-005 will used as the baseline area size of the target wound for SD-006. These unhealed target wounds from SD-005 will be assessed via ARANZ at each subsequent scheduled visit until the target wound is documented as closed. Closed wounds will be assessed for scarring.

STUDY OBJECTIVES

Primary Objective

The primary objective is to demonstrate the longterm safety of ZORBLISA in patients, with Simplex, Recessive Dystrophic, and Junctional non-Herlitz Epidermolysis Bullosa.

Secondary Objectives

The secondary objectives are to assess the efficacy of ZORBLISA in terms of the change in Body Surface Area (BSA) of lesional skin and wound burden; as well as closure of unhealed target wounds from the SD-005 study.

PLANNED SAMPLE SIZE

PATIENT POPULATION Inclusion Criteria

Up to approximately 150 patients are expected to roll over from Study SD-005 into this open-label extension.

- 1. Informed Consent form signed by the subject or subject's legal representative; if the subject is under the age of 18 but capable of providing assent, signed assent from the subject.
- 2. Subject (or caretaker) must be willing to comply with all protocol requirements.
- 3. Patients who completed the SD-005 study (on study drug at Visit 5).

Investigational product: Zorblisa™ (SD-101-6.0)	CONFIDENTIAL	Protocol No.: SD-006 Scioderm, Inc.
PATIENT POPULATION Exclusion Criteria	(A urine pregnancy t the final visit for SD of childbearing poter 1 if these visits do no	eeding during the study. est will be performed at -005 for female patients ntial and repeated at Visit ot occur on the same day) ing potential who are not ticing a medically
FORMULATION/DOSE	ZORBLISA (containing	6% allantoin)
ROUTE OF ADMINISTRATION	Topical	
DURATION/FREQUENCY OF TREATMENT	Once daily for 1440 days	s (48 months).
SAFETY ASSESSMENTS	The safety of ZORBLISA monitoring tolerability at adverse events, and perio examinations.	the application sites,
STATISTICAL CONSIDERATIONS	In general, results will be descriptive statistics. Ad be made to compare resp extension study with thei	ditional evaluations may onses of patients in this

2.		TABLE	OF CONTENTS	PAGE
1.	PROTO	DCOL SY	NOPSIS	2
2.	TABLE	E OF CO	NTENTS PAGE	5
3.	LIST O	F ABBR	EVIATIONS	7
4.	ADMI	NISTRAT	TIVE STRUCTURE	8
5.	BACK	GROUNI	D INFORMATION	9
	5.1.		w of Active Ingredient and Drug Product Formulation (SD-101)	9
		5.1.1. 5.1.2.	Pharmacology of Allantoin Pharmacokinetics of Allantoin	
		5.1.3.	SD-101 Topical Cream	
	5.2.		y of Animal and Human Studies with SD-101	
6.	RATIO	NALE F	OR STUDY	11
7.	STUDY		TIVES AND PURPOSE	
	7.1.		Objective	
	7.2.	Seconda	ry Objective	11
8.	SELEC		ND WITHDRAWAL OF PATIENTS	
	8.1.	5	Numbers	
	8.2. 8.3.		n Criteria	
	8.3. 8.4.		on Criteria wal Criteria/Study Discontinuation	
	8.5.		g of Withdrawals	
9.	STUDY	V DESIG	N AND ENDPOINTS	13
).	9.1.		esign	
	9.2.	Primary	Endpoint	13
	9.3.		ry Endpoints	
		9.3.1.	9.3.1.1. Definition of Lesional Skin for Assessment and	
		0.2.2	Calculation of BSA Coverage	
		9.3.2.	Change in Total Body Wound Burden Compared to Baseline 9.3.2.1. Definition of Wound for Assessment and	14
			Calculation of BSA Coverage	
		9.3.3.	Assessment of Closure of Target Wounds Non-Healed from	
			Study SD-005	15

5. BACKGROUND INFORMATION

Epidermolysis Bullosa (EB) is a rare group of inherited disorders that typically manifest at birth as blistering and lesion formation on the skin and, in some cases, the epithelial lining of other organs, in response to little or no apparent trauma. In consequence, the skin is extremely fragile which can result in shearing of the skin, causing a high risk of infection. All forms of EB are both debilitating and life threatening (see Appendix 1 Epidermolysis Bullosa Subtypes). In some EB subtypes, high mortality occurs before the age of 1 (Junctional Herlitz), and others in adolescences to early adulthood, typically due to infection or failure to thrive. In addition, children surviving into their 20's and 30's are also at risk for development of a virulent form of squamous cell carcinoma, which is in many cases fatal.

There are no standard of care products available to treat the dermal manifestations of EB, and there is no approved drug for EB in either Europe or the United States. There have been numerous studies published on potential treatments for skin manifestations associated with EB, including vitamin E therapy, systemic phenytoin, topical nonsteroidal agents, cyproheptadine, tetracycline, and dapsone. No controlled studies showed clinical benefit of any therapy. Newer exploratory treatments including skin grafts, bioengineered skin products, and gene therapy have been unsuccessful to date.

5.1. Overview of Active Ingredient and Drug Product Formulation (SD-101)

5.1.1. Pharmacology of Allantoin

The precise mechanism of action of allantoin in wound healing has not yet been defined. There are many animal wound and EB models, however, no product to date effective in any of these models has demonstrated effectiveness in humans. SD-101 was tested in the current appropriate wound model in EB, which is EB patients, and is the first product that has produced beneficial effects in healing of lesional skin, and appears to reduce the outbreaks of blistering. Data from the literature suggest that allantoin does not work via a single activity, but rather appears to affect multiple aspects of the processes involved in wound healing. These include reduction of inflammation, induction of growth of healthy tissue, stimulation of collagen as well as stimulation of granulation in ulcers, including tissue differentiation and epithelialization. In addition, allantoin has demonstrated bacteriostatic and bactericidal effects, and appears to aid in removing necrotic tissue.

5.1.2. Pharmacokinetics of Allantoin

Allantoin is a compound that is found endogenously in rats, rabbits, pigs, dogs, monkeys, in addition to a lower extent in humans. Allantoin is the main end product of purine metabolism in most mammals, and is produced from metabolism of uric acid via the enzyme, uricase. In rats and other mammals, uricase is present within peroxisomes of liver parenchymal cells. In man and great apes, uricase is not present, so that the primary end product of purine metabolism is uric acid. However, small amounts of allantoin are produced in great apes and humans via non-enzymatic conversion of uric acid.

5.1.3. SD-101 Topical Cream

Allantoin is the active ingredient contained within the SD-101 topical product, which is a commercially viable formulation with demonstrated stability of allantoin for several years at concentrations up to 9%. The capability to deliver the active moiety to the target in skin is key in topical products, since the skin is an effective barrier to penetration. In a series of flux studies

with SD-101 containing allantoin ranging from 0.5 to 9%, penetration across the various skin barriers was dose-related.

The SD-101 proprietary formulation has been developed to overcome the inherent limited solubility and stability of allantoin, allowing the ability to formulate allantoin at higher concentrations. In consequence, allantoin concentrations as high as 9% can be achieved in a topical product whereas the amount in existing cosmetics as an inactive excipient is typically less than 0.2%.

The SD-101 topical product is currently being developed as a new topical therapy for the treatment of lesional skin in patients with EB. The same product is foreseen for adult and pediatric patients.

5.2. Summary of Animal and Human Studies with SD-101

Toxicology studies assessing topical administration of SD-101-9.0 in multiple species demonstrated the lack of local or systemic effects with this active in the current formulation. The lack of systemic effects with allantoin in animals administered SD-101 (containing various concentrations of allantoin) topically was further supported by additional safety information obtained with intravenous administration of allantoin in the monkey. Peak intravenous blood levels in the monkeys were achieved that were approximately 700 times higher than endogenous levels measured in published healthy human subject pharmacokinetic studies, without any demonstrated clinical chemistry abnormalities or organ toxicity at either the macroscopic or microscopic level. Additional toxicology studies with SD-101-9.0 demonstrated that this product was non-sensitizing in the guinea pig and did not produce ocular irritation in the rabbit. Lastly, from examination of the excipients and the active ingredient, allantoin, for the ability to absorb light in the UV-A and/or UV-B ranges, there were no demonstrated concerns of potential phototoxicity with use of this product.

Studies in normal volunteers with topical use of SD-101 (SD-101-0.0, SD-101-3.0, SD-101-6.0, and SD-101-9.0), and in EB Patients with topical usage of SD-101 (SD-101-1.5, SD-101-3.0, and SD-101-6.0) demonstrated to date that allantoin at these concentrations (in this formulation) has not produced any local or systemic adverse effects of concern. In addition, topical administration of SD-101 (SD-101-1.5) was found to be non-sensitizing in healthy subjects.

An open-label study using SD-101-3.0 was previously conducted. Eight EB patients with a diagnosis of EB (Simplex, Recessive Dystrophic, or Junctional) based on diagnostic immunomapping or electron microscopy, were treated with SD-101-3.0 cream once applied daily to their entire skin surface, for a period up to 3 months. Application of the cream was non-irritating and did not produce any discomfort when applied to either unblistered areas or open lesions. The patients treated with SD-101-3.0 for three months showed significant improvements in the complete healing of lesions (typified by the results with the target wounds), clinically meaningful reductions in the extent of total skin surface involvement with active disease (body surface area [BSA]), and reduced pain and itching. Daily use of SD-101-3.0 cream in treatment up to 3 months was well tolerated by all patients in the study, with no related adverse events (AEs) noted. There were no serious AEs (SAEs) that occurred in any patient during the 3-month treatment period. In addition, there was good compliance on usage of the product on the entire skin surface, based on the soothing and non-irritating effects of the SD-101 creams.

A Phase 2B study (SD-003) was completed with two strengths of SD-101 (containing 3% and 6% allantoin: identified as SD-101-3.0 and SD-101-6.0) with a matching placebo control (SD-101-0.0). The primary endpoint of this study was the complete closure of the patient's target chronic wound within one month. Secondary endpoints comprised effects on improvement in body

CONFIDENTIAL

coverage in lesional skin (including blistering), pain, and itching. In addition, patients from Study SD-003 were offered to roll-over into an open-label extension study (Study SD-004) to continue treatment with SD-101-6.0 to collect long term safety data. The results of Study SD-003 support that SD-101-6.0 is the most efficacious and safe concentration. It is the concentration used in the registration study (SD-005) and compared against the placebo group receiving SD-101-0.0.

The design of studies SD-003 (Phase 2B) and SD-005 (Phase 3) are essentially identical, with differences in number of treatment arms and sample size, and minor modification of the minimum target wound size at study entry. Patients completing SD-005 are the population for this study.

6. RATIONALE FOR STUDY

The aim is to assess the long-term safety of ZORBLISA in the treatment of patients with Epidermolysis Bullosa.

7. STUDY OBJECTIVES AND PURPOSE

7.1. **Primary Objective**

The primary objective is to demonstrate the long-term safety of ZORBLISA in patients with Simplex, Recessive Dystrophic, and Junctional non-Herlitz Epidermolysis Bullosa.

7.2. Secondary Objective

The secondary objectives are to assess the efficacy of ZORBLISA in terms of the change in Body Surface Area (BSA) of lesional skin and wound burden; as well as assessment of closure of unhealed target wounds in patients rolling over from the SD-005 study.

8. SELECTION AND WITHDRAWAL OF PATIENTS

8.1. Subject Numbers

Approximately 150 EB patients will be enrolled at study sites worldwide, following completion of their participation in Study SD-005.

8.2. Inclusion Criteria

Patients must meet all of the following inclusion criteria to be eligible for enrollment into the study.

- 1. Informed Consent form signed by the subject or subject's legal representative; if the subject is under the age of 18 but capable of providing assent, signed assent from the subject.
- 2. Subject (or caretaker) must be willing to comply with all protocol requirements.
- 3. Patients who completed the SD-005 study (on study drug at Visit 5).

8.3. Exclusion Criteria

Patients with any of the following exclusion criteria will not be eligible for enrollment into the study.

- 1. Patients who do not meet the entry criteria outlined above.
- 2. Pregnancy or breastfeeding during the study. (A urine pregnancy test will be performed at the final visit for SD-005 for female patients of childbearing potential and repeated at Visit 1 if these visits do not occur on the same day)
- 3. Females of childbearing potential who are not abstinent or not practicing a medically acceptable method of contraception.

8.4. Withdrawal Criteria/Study Discontinuation

Patients may withdraw from the study at any time without stating a reason and without prejudice to further treatment. The Investigator may withdraw a subject from the study and discontinue study treatment and assessments at any time due to safety concerns. Full skin examination will be performed at each visit. If ZORBLISA causes any significant rash that has not occurred previously in the subject, the Investigator should consider discontinuing the subject. In addition, if lesions appear to significantly worsen above the normal cycle seen in the patient, with use of ZORBLISA, the investigator should consider discontinuing the subject.

Early discontinuation of any subject who has given informed consent /assent to participate will be recorded including the reason for discontinuation. The primary reason for a subject withdrawing prematurely will be selected from the following standard categories of early discontinuations.

- 1. Adverse Event and Adverse Reactions: Clinical events occurred that are reported that in the medical judgment of the investigator are grounds for discontinuation in the best interests of the subject.
- 2. Withdrawal of Consent: The subject desired to withdraw from further participation in the study. The subject is not obligated to provide any reason for withdrawal of consent, but where a reason is given this will be recorded on the eCRF.
- 3. Protocol Violation: The subject failed to adhere to the protocol requirements, at the investigator's discretion.
- 4. Lost to Follow-Up: The subject stopped coming for visits and study personnel were unable to contact the subject.
- 5. Other: The subject was terminated for a reason other than those listed above, such as, termination of study by Sponsor.

8.5. Handling of Withdrawals

Although a subject is not obligated to give his/her reason for withdrawing prematurely, the Investigator will make a reasonable effort to obtain the reason while fully respecting the subject's rights. In the case of withdrawal due to an adverse event the subject will be followed per Section 13.3. Reasonable efforts will be made to contact a subject who fails to attend any follow-up appointments, to ensure that he/she is in satisfactory health.

9. STUDY DESIGN AND ENDPOINTS

9.1. Study Design

This is an open label, multi-center extension study to assess the long-term safety of ZORBLISA in treating patients with Simplex, Recessive Dystrophic, and Junctional non-Herlitz Epidermolysis Bullosa. All patients must have completed SD-005 to be eligible to participate in this open label extension.

ZORBLISA will be applied topically, once a day, to the entire body for a period of 1440 days. Patients will return to the study site at Month 1, then once every 3 months until Month 48 (Months 3, 6, 9, 12, 15, 18, 21, 24, 27, 30, 33, 36, 39, 42, 45, and 48).

9.2. Primary Endpoint

The primary endpoint is the long-term safety of ZORBLISA in patients with Simplex, Recessive Dystrophic, and Junctional non-Herlitz Epidermolysis Bullosa. Safety is assessed via monitoring of local tolerability at the application sites, occurrence of adverse events and physical examinations.

9.3. Secondary Endpoints

The secondary endpoints include the change from baseline in BSA coverage of lesional skin and wound burden; as well as closure of unhealed target wounds from the SD-005 study.

9.3.1. Change from Baseline of Body Surface Area of Lesional Skin

Change in lesional skin based on BSA estimates at Months 1, 3, 6, 9, 12, 15, 18, 21, 24, 27, 30, 33, 36, 39, 42, 45, and 48 compared to Baseline will be measured using the Body Surface Area Index (BSAI). The BSAI is a global measure of disease extent with weighting factors. The BSA affected with lesional skin will be calculated at baseline and at each visit to assess the total affected area before and after using the product. The BSA will be assessed as in Figure 9-1 per the definition below by a study physician. Preferably the same study physician will perform this assessment at each patient visit.

9.3.1.1. Definition of Lesional Skin for Assessment and Calculation of BSA Coverage

- Consists of area(s) that could contain any of the following: blisters, erosions, ulcerations, scabbing, bullae, and eschars, as well as areas that are weeping, sloughing, oozing, crusted, and denuded.
 - Percent of this area recorded for each defined body region (number from 0-100% assigned for each region) BSA

Note: Coloration should not lead to misinterpretation of whether a lesion is active. Erythema and hyper- or hypo-pigmentation do not necessarily indicate that a lesion is active, and in fact can be found in healed or scarred skin that would not be added to BSAI calculation of lesional skin coverage, unless it meets the definition above.

• Other areas categorized as skin that is either healed or scarred are not considered lesional skin.

Figure 9-1: BSAI of Lesional Skin Calculation Charts

(Check only one box and complete the appropriate sections for each region)								
1 🗆 Ag	1							
Column 1	Column 2	Column 3	Column 4	Column 5				
Region Number	Region Description	Regional BSA % that is affected*	Weighting Factor	Total BSA % that is affected **				
1	Head / Neck		x .2					
2	Upper Limbs		x .2					
3	Trunk (includes groin)		x .3					
4	Lower Limbs		x .3					
			TOTAL					

2 🗆 Age 8 years or greater

Column 1	Column 2	Column 3 Column 4		Column 5
Region Number	Region Description	Regional BSA % that is affected*	Weighting Factor	Total BSA % that is affected **
1	Head / Neck		x .1	
2	Upper Limbs		x .2	
3	Trunk (includes groin)		x .3	
4	Lower Limbs		x .4	
·			TOTAL	

* For each region, enter the % of BSA that is affected with lesional skin. Score each region separately from 0% - 100%.

** Multiply the value in Column 3 by the factor in Column 4. The Total value at the bottom of the table is the sum of Column 5 values for each region.

9.3.2. Change in Total Body Wound Burden Compared to Baseline

Change in total body wound coverage based on BSA estimates at Months 1, 3, 6, 9, 12, 15, 18, 21, 24, 27, 30, 33, 36, 39, 42, 45, and 48 compared to Baseline will be measured using the BSAI. Using the same principles that underlie the BSAI estimates of lesional skin, the percentage of the total BSA affected by open wounds will be calculated to assess the total wound area before and after using the product. The BSA of wounds will be assessed by a study physician as per Figure 9-2. Preferably the same study physician will perform this assessment for each patient visit.

9.3.2.1. Definition of Wound for Assessment and Calculation of BSA Coverage

A wound is defined as an open area on the skin (epidermal covering is disrupted).

Figure 9-2: BSAI of Total Wound Burden Calculation Charts

(Check only one box and complete the appropriate sections for each region) 1						
Column 1	Column 2	Column 3	Column 4	Column 5		
Region Number	Region Description	Regional BSA % that is affected*	Weighting Factor	Total BSA % that is affected **		
1	Head / Neck		x .2			
2	Upper Limbs		x .2			
3	Trunk (includes groin)		x .3			
4	Lower Limbs		x .3			
			TOTAL			

2 🗆 Age 8 years or greater

Column 1	Column 2	Column 3	Column 4	Column 5
Region Number	Region Description	Regional BSA % that is affected*	Weighting Factor	Total BSA % that is affected **
1	Head / Neck		x .1	
2	Upper Limbs		x .2	
3	Trunk (includes groin)		x .3	
4	Lower Limbs		x .4	
 			TOTAL	

* For each region, enter the % of BSA that is affected with open wounds. Score each region separately from 0% - 100%.

** Multiply the value in Column 3 by the factor in Column 4. The Total value at the bottom of the table is the sum of Column 5 values for each region.

9.3.3. Assessment of Closure of Target Wounds Non-Healed from Study SD-005

For target wounds that are not closed by the end of Study SD-005, the ARANZ picture and calculation of target wound area at the final visit for Study SD-005 will be used as the baseline area size of the target wound for SD-006. The unhealed target wound from SD-005 will be

assessed via the ARANZ SilhouetteStar[™] at each subsequent scheduled visit until the target wound is documented as closed. The closed target wound will be assessed for scarring.

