- e. If the target wound has not healed by the final visit of the SD-005 study, the target wound will be assessed in SD-006 using ARANZ until the wound has healed. The ARANZ picture and target wound area value determined at the final visit for SD-005 will be utilized as the baseline target wound area and picture for SD-006 unless Visit 1 is ≥ 14 days after the final SD-005 visit, in which case the assessment will be repeated. If target wound has healed, assess for scarring.
- f. The urine pregnancy test performed at the final visit for SD-005 will be utilized for entry into SD-006 if the visits occur on the same day. Otherwise, the urine pregnancy test will be performed at Visit 1 and at Visits 3 through 18.
- g. Ensure the patient is dispensed sufficient ZORBLISA until the next study visit.
- h. All AEs experienced in SD-005 should be noted in medical history for SD-006 at Visit 1 only.

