14.3. Analysis Considerations

In general, results will be summarized using descriptive statistics. Summary statistics to be used include proportion of patients with complete closure of their target lesion at each visit, mean and standard deviation of BSAI compared with baseline at each visit, and incidence rates of specific adverse events.

Additional evaluations may be made to compare responses of patients in this extension study with their responses in SD-005. For those patients randomized to ZORBLISA in SD-005, the use of summary statistics as described in the previous paragraph will provide an understanding of the long term effect of ZORBLISA in these patients. For those patients randomized to the control arm in SD-005, summary statistics will be used to compare their response to ZORBLISA in SD-006 with their response to control in SD-005.

In addition to the evaluations described above for the primary efficacy and safety variables, secondary and exploratory variables will also be evaluated using summary statistics.

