4. STUDY DESIGN

4.1. General Design

This is an open label, multi-center extension study to assess the long-term safety of SD-101-6.0 in treating patients with Simplex, Recessive Dystrophic, and Junctional non-Herlitz epidermolysis bullosa.

SD-101-6.0 will be applied topically, once a day, to the entire body for a period of 1440 days (48 months). This study may be further extended by amendment until either SD-101 becomes commercially available or the clinical development of SD-101 in EB is discontinued.

Patients who successfully completed Study SD-005 (on study drug at Visit 5) have had the option to roll over into the SD-006 study. The baseline visit (Visit 1) has occurred at Visit 5 for SD-005. The Body Surface Area Index (BSAI) assessments of lesional skin and wound burden performed at the final Visit for SD-005 are to be utilized as the baseline assessment for SD-006 unless Visit 1 is ≥ 14 days after the final SD-005 visit in which case the assessment are to be repeated. Patients return for follow-up visits at Months 1, 3, 6, 9, 12, 15, 18, 21, 24, 27, 30, 33, 36, 39, 42, 45, and 48 after Visit 1. At each visit, assessments include BSAI of lesional skin and wound burden. The unhealed target wounds from SD-005 are assessed at each subsequent scheduled visit until the target wound is documented as closed. Closed wounds will be assessed for scarring.

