4.2. Method of Assignment of Patients to Treatment Groups

There will only be one treatment group so patients will not be randomized to treatment. All patients will receive SD-101-6.0.

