6.3. Baseline Definition and Assessments

6.3.1. Baseline definition

For most cases, the baseline visit (Visit 1) will occur at Visit 5 for SD-005. Exceptions are detailed below.

The Body Surface Area Index (BSAI) assessments of lesional skin and wound burden performed at the Visit 5 for SD-005 will be utilized as the baseline assessment for SD-006 unless Visit 1 is ≥ 14 days after the final SD-005 visit in which case the assessment will be repeated.

The urine pregnancy test performed at the final visit for SD-005 will be utilized for entry (Visit 1) into SD-006 only if the visits occur on the same day, otherwise, urine pregnancy test will be performed at Visit 1 as baseline assessment for SD-006.

The physical examination performed at the final visit for SD-005 will be utilized as the baseline assessment for SD-006 unless Visit 1 is ≥ 14 days after the final SD-005 visit, in which case a physical examination will be repeated and used as baseline assessment for SD-006.

The ARANZ picture that documents target wound status at the final visit for SD-005 will be utilized to determine target wound area unless Visit 1 is ≥ 14 days after the final SD-005 visit, in which case the assessment will be repeated on the same wound. For target wounds that are not closed by the end of Study SD-005, the ARANZ picture and calculation of target wound area at the final visit for Study SD-005 will be used as the baseline area size of the target wound for SD-006. The wounds that are closed at the end of study SD-005 will not be followed up and analyzed.

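### Target-wound assessment ends at first documented closure and omits wounds closed at entry, so re-opening is not recorded and the share actually closed at each visit cannot be computed

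*Protocol*

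**What the plan says.** Closure of target wounds left unhealed by SD-005 is a secondary endpoint (Protocol 9.3). Four statements bear on how it is observed.

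- **When assessment stops.** Protocol 9.3.3 has the wound measured "at each subsequent scheduled visit until the target wound is documented as closed". Footnote e to the Protocol section 11 schedule agrees: "the target wound will be assessed in SD-006 using ARANZ until the wound has healed". So does SAP 4.1: "The unhealed target wounds from SD-005 are assessed at each subsequent scheduled visit until the target wound is documented as closed".
- **Who is left out.** SAP 6.3.1: "The wounds that are closed at the end of study SD-005 will not be followed up and analyzed".
- **What happens after closure.** Protocol 9.3.3: "The closed target wound will be assessed for scarring". Neither document says when or how often. Neither defines re-opening, recurrence or confirmed closure.
- **What is to be reported.** Protocol 14.3 lists the "proportion of patients with complete closure of their target lesion at each visit". It gives no denominator and no rule for carrying a closure forward.

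SAP section 3 keeps healing of these wounds as an objective, but SAP 8.6 contains only BSAI analyses. SAP Table 1 and its footnote e add that target-wound data were not captured at the Month 48/end-of-study visit.

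**The concern.** A proportion closed at each visit is a statement about wound status at that visit. Once a wound has been documented closed, its later status is not collected, so the planned statistic and the data collection do not fit together. What the data can support is whether a wound was ever documented closed, and when that was first seen.

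The two quantities differ whenever closed wounds re-open, and Protocol section 5 describes the skin in this disease as extremely fragile. In a 48-month extension the natural question about closure is whether it lasts. An ever-closed percentage presented as the percentage closed would suggest an answer that the data do not contain. Omitting wounds closed at entry removes a further group in which loss of closure could have been seen, and makes the assessed set start at 0% closed by construction.

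Adverse-event reporting is not a dependable substitute, since Protocol 13.3.1 says changes in the disease condition may not qualify as AEs.

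**Working it through.** The documents state no closure rate, re-opening rate or expected closure proportion, so there is no plan figure to reproduce. The calculation below only shows how far the two quantities can separate.

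**Inputs**

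- Number of target-wound visits, K. Post-baseline visits are Visits 2 to 18, which is 17. Month 48/end of study was not captured (SAP Table 1, footnote e), leaving Visits 2 to 17, so K = 16 at most.
- Chance p that an open wound is found closed at the next visit: assumed 5%, 10%, 20%.
- Chance b that a closed wound is found open at the next visit: assumed equal to p, then zero.
- All wounds open at SD-006 entry, as SAP 6.3.1 implies. Chances constant over time.

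**Formulas**

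- Ever documented closed by visit K: 1 − (1 − p)^K.
- Actually closed at visit K: p/(p + b) × [1 − (1 − p − b)^K].

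**Results, K = 16**

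| p | Ever closed | Actually closed, b = p | Gap (points) |
|---|---|---|---|
| 5% | 1 − 0.95^16 = 56.0% | 0.5 × (1 − 0.90^16) = 40.7% | 15.3 |
| 10% | 1 − 0.90^16 = 81.5% | 0.5 × (1 − 0.80^16) = 48.6% | 32.9 |
| 20% | 1 − 0.80^16 = 97.2% | 0.5 × (1 − 0.60^16) = 50.0% | 47.2 |

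With b = 0 the second formula reduces to the first, and the gap is zero.

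**Check with the real visit spacing.** The intervals are 1 month, 2 months, then fourteen of 3 months up to Month 45. Assume closing and re-opening rates of 0.10 per month each. The chance that an open wound is found closed after t months is 0.5 × (1 − e^(−0.2t)): 0.0906, 0.1648 and 0.2256 for t = 1, 2 and 3.

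- Ever closed at Month 45: 1 − 0.9094 × 0.8352 × 0.7744^14 = 97.9%.
- Actually closed at Month 45: 0.5 × (1 − e^(−9)) = 50.0%.
- At Month 12 the same comparison gives 64.7% against 45.5%.

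**Dependence on the unstated denominator.** The ever-closed figure cannot fall only if closures are carried forward over a fixed set of patients. Under the same 0.10 rates, other readings behave differently:

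- New closures over a fixed N without carry-forward peak at 17.1% at Month 6 and drop to 0.6% at Month 45.
- Closures among wounds still under assessment stay at 22.6% per 3-month interval.
- With attending patients as denominator, 20/40 (50%) becomes 10/30 (33%) if ten patients with closed wounds leave.

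None of these is the share of target wounds closed at that visit.

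**Effect of keeping wounds closed at entry.** With 50% closed at entry (assumed) and equal rates, the share closed stays at 50% throughout. The rise from 0% therefore comes from who is assessed, not from any change in the disease.

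**The case against.** The strongest reply is that the stated aim is closure of wounds that SD-005 left open, and follow-up to first closure answers that. Neither document promises durable closure, the primary objective is safety, and efficacy is mostly descriptive. This stands as far as first closure goes, but Protocol 14.3 asks for a proportion at each visit, and first-closure data do not supply it.

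A reader might infer several stronger things that the documents do not support.

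- *The closure figure can only rise.* That needs a cumulative count on a fixed denominator, which is not written. SAP 7.1 (population denominator) and SAP 7.3 (no imputation), read literally, would allow it to fall.
- *Everything that counts against the drug goes unobserved.* Enlargement of an open target wound is measured by ARANZ, and a re-opened wound enters BSAI wound burden at each visit. What is missing is identification of the target wound itself.
- *Only wounds closed at entry could show loss of effect.* A wound that closes during SD-006 can also re-open.
- *The stopping rule is why an active cream cannot be told from an inactive one.* The main reason is the single arm: "There will only be one treatment group so patients will not be randomized to treatment". Even with continued follow-up, an inactive cream in the illustration takes wounds open at entry from 0% to between 41% and 50%.
- *A closure is to be expected without drug.* The mention in Protocol 8.4 of a normal cycle of lesions gives no closure rate for target wounds, and this cohort is selected for not having closed.

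The timing objection also has force. SAP 5.1 records that sites were told in June 2018 to stop application and hold end-of-study visits, so 16 visits is a ceiling and many patients will have fewer. For data already collected, only the reporting can change.

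**Conclusion.** The point holds in a bounded form. Re-opening of target wounds is not captured in the target-wound endpoint, so the per-visit statistic in Protocol 14.3 cannot be obtained as the share actually closed. A cumulative count on a fixed denominator would overstate current closure by 15 to 47 points in the illustration at 16 visits, and by nothing if wounds never re-open. The rates are assumptions held constant in time, and the data as collected cannot show which case applies. The size is therefore illustrative, while the mismatch between endpoint and data collection is textual and does not depend on it. It is worth correcting as a matter of design and labelling. It does not bear on the primary safety objective, and it does not show that any closure result is wrong.

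**What to change.** In Protocol 9.3.3 and schedule footnote e, record the target-wound site as open or closed at every visit for all patients with an SD-005 target wound, including after closure and for wounds closed at entry. Delete the exclusion in SAP 6.3.1. Report, by SD-005 group, the share closed at each visit among observed target wounds, and re-opening among closed wounds.

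The cost is one field at visits where, by Protocol 8.4, "Full skin examination will be performed at each visit", and where healed wounds are in any case due a scarring check. The downside for the sponsor is a less favourable closure figure.

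For data already collected under the present rule, any closure result should be labelled first documented closure and given a stated denominator. It should carry the statement that durability is unknown and make no claim of lasting closure. That costs only wording. Neither step supplies a control, so closure should be presented as descriptive in either case.
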